12 breaths (6 to 72 mcg) four times daily to achieve daily doses of 24 to 288 mcg. The longest duration of inhaled treprostinil exposure in the open-label study was 5.4 years and the mean duration 2.3 years. There were observed improvements in median 6MWD at 6, 12, 18 and 24 months of 28, 31, 32 and 18 meters, respectively. These data support the durability of improvement in 6MWD obtained with inhaled treprostinil as demonstrated during the doubleblind phase of the study. Therapeutic benefit was also noted with improvements in the Borg dyspnea score, NYHA functional classification and quality of life (QOL). Survival was robust with one and two year Kaplan-Meier survival estimates of 97% and 91%, respectively, for subjects that remained in the trial. The most frequently reported AEs during the openlabel study were cough (39%), headache (31%), upper respiratory tract infection (22%), and nausea (22%). There were no clinically significant changes in clinical chemistry or hematology parameters. Unique findings that related to the inhaled route of administration, in addition to cough, were throat pain and throat irritation, occurring in 12% and 10% of subjects, respectively. These events were usually of mild or moderate severity and transient in duration. In a few subjects, these specific AEs were more pronounced as six subjects (3%) discontinued inhaled treprostinil due to cough, including one subject (<1%) with dry throat (Benza 2011).

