#### 4.3 PRESCRIBED THERAPY

In this open-label study, there are no restrictions on concomitant medications with the exception of the permanent addition (29 days or more) of infused prostacyclin therapy. Subjects who receive permanent infused prostacyclin therapy must discontinue this open-label study.

All concomitant medications taken during the conduct of the study, including those taken for AEs or other medical events, should be recorded in the subject's source documents and transcribed into the eCRF as required. The flow rate of supplemental oxygen should be recorded as outlined in Section 3.3.2.5.2.

Subjects who initiate pulmonary rehabilitation during the course of the study should also record this information in the eCRF.

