#### 7.3 WEEK 108 / STUDY TERMINATION VISIT

The Week 108 visit will be the Study Termination Visit. In addition, if a subject discontinues the study prior to Week 108, they will complete a Study Termination Visit. If possible, each subject should remain on study drug until they have completed the Study Termination Visit. The following assessments will occur at the Study Termination Visit:

- SGRQ (questionnaire must be administered prior to any results, procedures, or blood draws)
- Physical examination
- Vital signs (following at least five minutes of rest; collected prior to 6MWT or after recovery from the 6MWT)
- Urine pregnancy test, for women of childbearing potential
- Blood draws for clinical laboratory parameters
- NT-proBNP (must be drawn prior to 6MWT)
- Collection of blood sample for evaluation of biomarkers (optional; only in those subjects who discontinue prior to Week 48)

\*Assessments conducted during the Week 48 visits ONLY.

- Peak 6MWT (must be conducted between 10 to 60 minutes after the most recent dose of study drug and following at least 10 minutes of rest [sitting])
- Pulse oximetry (to be performed immediately prior to, throughout the conduct of, and immediately following the 6MWT)
- Documentation of supplemental oxygenation requirement (L/min)
- PFTs (to be performed after recovery from the 6MWT)
- Hospitalizations due to a cardiopulmonary indication
- Exacerbations of underlying lung disease
- Adverse events
- Concomitant medications
- Study drug accountability

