8.2 PREMATURE DISCONTINUATION AND MISSING DATA

A subject may voluntarily withdraw or be withdrawn from the study and/or study drug by the Investigator at any time for reasons including, but not limited to, the following:

- The subject wishes to withdraw from further participation.
- A serious or life-threatening AE occurs or the Investigator considers that it is necessary to discontinue study drug to protect the safety of the subject.
- The subject consistently deviated from the protocol.
- The subject's behavior is likely to undermine the validity of his/her results.
- The subject permanently initiates an infused prostacyclin therapy for >29 days.
- The subject becomes pregnant.

All available data from all subjects in the Safety Population, as defined in Section 7, will be used as detailed in this analysis plan.

Missing data will not be imputed.

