8.5 DERIVED AND TRANSFORMED DATA

The time to event will be calculated for each of the following variables as detailed in

Table 8-2:

- Hospitalization due to a cardiopulmonary indication
- Exacerbation of underlying disease
- Death

Table 8-2 Derivation of Time to Event

Parameter	Scenario	Formula	Status
Time to hospitalization (weeks)	Subjects with hospitalization during the study	= (Hospitalization date – first visit date +1)/7	0 (event)
	Subjects without hospitalization during the study	= (Last assessment date – first visit date +1)/7	1 (censored)
Time to exacerbation (weeks)	Subjects with exacerbation during the study	= (Exacerbation date – first visit date +1)/7	0 (event)
	Subjects without exacerbation during the study	= (Last assessment date – first visit date +1)/7	1 (censored)
Time to death (weeks)	Subjects who died during the study	= (Death date – first visit date +1)/7	0 (event)
	Subjects who completed or discontinued prematurely	= (Last assessment date – first visit date +1)/7	1 (censored)

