9 STUDY POPULATION

9.1 SUBJECT ACCOUNTABILITY

A listing of subject disposition and inhaled treprostinil exposure will include subject number, treatment group in the parent study, first and last inhaled treprostinil dose date/time in the RIN-PH-202 study, date completed/discontinued the study, cut-off date, study drug exposure (weeks), reason for discontinuation, and any other details regarding reason for discontinuation. The summary of subject accountability will include the number (percent) of subjects by treatment group who completed the study without early termination, the number of subjects who completed inhaled treprostinil treatment by each visit achieved, the number of subjects who discontinued inhaled treprostinil treatment, and the reason for discontinuation. This summary will be provided by treatment group in the parent study and overall.

Inhaled treprostinil exposure and the total subject-years of inhaled treprostinil exposure will be summarized by treatment group in the parent study and overall.

In addition, for subjects who were in the inhaled treprostinil treatment group in the parent study (RIN-PH-201), their exposure to inhaled treprostinil in the parent study will be combined with the RIN-PH-202 study. The overall exposure to inhaled treprostinil across both the parent study and the RIN-PH-202 study will be summarized.

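### Time to death censors every premature discontinuer alike, including health-related exits, and no planned analysis shows how far this could move the survival curve

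*SAP*

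**What the plan says.** SAP 8.5, Table 8-2, gives two rows for time to death. "Subjects who died during the study" are events at the death date. "Subjects who completed or discontinued prematurely" are censored at the last assessment date. The second row combines subjects who reach Week 108, those whose participation ends administratively, and everyone who leaves early for any reason.

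Some of those reasons concern health. Protocol 4.3 states: "Subjects who receive permanent infused prostacyclin therapy must discontinue this open-label study". SAP 8.2, repeating Protocol 8.1, lists "A serious or life-threatening AE occurs or the Investigator considers that it is necessary to discontinue study drug" to protect the subject, and "The subject permanently initiates an infused prostacyclin therapy for >29 days". These lists are open-ended and permissive. Clinical worsening is not named in them.

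Protocol 7.3 provides that "if a subject discontinues the study prior to Week 108, they will complete a Study Termination Visit". No scheduled vital-status follow-up comes after that visit. SAEs are followed to resolution or death (Protocol 3.3.2.6), so some later deaths may become known. Protocol 9.3 keeps events on commercial drug after withdrawal out of the protocol analysis.

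SAP 11.2 plans Kaplan-Meier estimates by parent-study group and overall, and an optional Cox model with parent-study group as explanatory variable. The same section counts deaths up to 30 days after the last dose in premature discontinuers, in the death listing and the death summary. SAP 9.1 lists "reason for discontinuation, and any other details regarding reason for discontinuation" and summarises the reasons. SAP 8.2 leaves missing data unimputed.

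**The concern.** Kaplan-Meier and Cox estimates are valid when subjects censored at a given time have the same later risk as those still followed. That is reasonable for subjects who reach Week 108 or stop because the study ends. It is doubtful for subjects who leave because of a serious AE, an Investigator's safety decision or a move to permanent infused therapy. One row treats all of these alike.

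The result would be read as survival on long-term treatment in an uncontrolled extension whose secondary objective is long-term safety and efficacy. The protocol attaches the limitation to the earlier PAH extension: its 97% and 91% one- and two-year estimates are given "for subjects that remained in the trial" (Protocol 1.2.3). The SAP puts no such qualifier on its own curve (Figure 14.3.1). Nothing in SAP 8.5, SAP 11.2 or the SAP 12 output lists tests the assumption or bounds its effect.

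**Working it through.** **No planned figure to reproduce.** The documents give no survival target, event count, exit rate or post-exit mortality. The 266 subjects are an expected enrolment without a calculation. All rates below are therefore assumptions, and the results illustrate size only.

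**Model.** Constant hazards, t = 2 years.
- L: death hazard while in study.
- d: hazard of health-related exit, d = -ln(1 - p)/t, where p is the proportion who would exit by 2 years in the absence of death.
- k: death hazard after exit divided by L.

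Under Table 8-2, Kaplan-Meier converges to exp(-L·t). Actual survival, counting deaths after exit, is

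S = exp(-(L+d)t) + d·exp(-kLt)·[1 - exp(-(L+d-kL)t)]/(L+d-kL).

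For each assumed S, p and k, solve for L. The bias is exp(-L·t) - S.

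**Worked cases, S = 75%.**
- p = 10%, k = 2: d = 0.0527 and L = 0.1374. Check: 0.684 + 0.066 = 0.750. Kaplan-Meier gives exp(-0.2748) = 76.0%, which is 1.0 point too high.
- p = 30%, k = 4: d = 0.1783 and L = 0.1023. Check: 0.571 + 0.179 = 0.750. Kaplan-Meier gives exp(-0.2045) = 81.5%, which is 6.5 points too high.

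**Overstatement at 2 years, percentage points.**

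| Actual survival | p=10%, k=2 | p=10%, k=4 | p=20%, k=2 | p=20%, k=4 | p=30%, k=2 | p=30%, k=4 |
|---|---|---|---|---|---|---|
| 65% | 1.2 | 2.8 | 2.4 | 5.5 | 3.6 | 8.1 |
| 75% | 1.0 | 2.4 | 1.9 | 4.5 | 2.8 | 6.5 |
| 85% | 0.6 | 1.6 | 1.3 | 3.1 | 1.9 | 4.3 |
| 91% | 0.4 | 1.1 | 0.8 | 2.0 | 1.2 | 2.7 |

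The 91% row borrows the only 2-year survival figure in the documents. It comes from a different population (PAH) and is illustrative only.

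**Direction.** At k = 1 the bias is zero in every row. At k = 0.5 it reverses: with p = 20%, Kaplan-Meier is too low by 1.2 points at 75% survival and by 0.5 points at 91%.

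**Lower bound.** If every health-related exit counts as an event on the exit date, the curve converges to exp(-(L+d)t) = exp(-L·t)·(1 - p). For S = 75% the values on the grid run from 0.7785 × 0.70 = 54.5% to 0.7738 × 0.90 = 69.6%. No planned output reports this quantity.

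**Does the 30-day count close the gap?** Assume 75% on-study 2-year survival, 20% exits by Week 108 and k from 2 to 10, with last dose and exit on the same day. Then about 9% to 15% of post-exit deaths before Week 108 fall within 30 days of exit, so the count does not bound the bias. It also exposes an ambiguity. A subject who stops early and dies on day 20 appears in the SAP 11.2 death summary, but Table 8-2 does not define the study period for death. The subject fits the event row or the censoring row depending on how that is read, so the death table and the curve can disagree.

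**A related mismatch.** Protocol 4.3 defines permanent infused therapy as 29 days or more, while Protocol 8.1 and SAP 8.2 say more than 29 days. The passages must be reconciled before exits are classified.

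**The case against.** The strongest reply is that the direction is not known. A reader might infer that the survival curve is optimistic as a matter of fact. The documents do not support that: they say nothing about the death rate after exit, and infused therapy could itself change the hazard. This stands, and the bias is therefore stated conditionally.

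A reader might also infer that the sickest subjects are removed by rule. Only the infused-prostacyclin exit is mandatory. The AE item is permissive, and deterioration is not a listed reason. If only 5% left, the overstatement at 75% survival would be 0.5 points (k = 2) to 1.2 points (k = 4). Nor are those who leave counted as alive at Week 108. They drop out of the risk set at their own last assessment, and the issue is the assumption made about them afterwards.

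The plan also has partial safeguards: reasons for discontinuation, AEs leading to permanent discontinuation, the 30-day death count, and separate Kaplan-Meier outputs for hospitalization and exacerbation. These are useful, but none connects exits to the survival curve.

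Finally, the weight is limited. The primary objective is drug access, death is not a listed endpoint, no hypothesis is tested and the Cox model is optional. This also stands. The point concerns how a descriptive curve is read.

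**Conclusion.** The point holds in a limited form. Censoring in Table 8-2 ignores the reason for exit, at least one health-related exit is mandatory, and no planned analysis tests or bounds the consequence. Whether the curve is too high depends on whether subjects who leave die faster than those who stay. That is plausible for the exits named, but the documents do not show it.

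The overstatements of about 1 to 8 points (true survival 65% to 75%) and 0.4 to 4.3 points (85% to 91%) rest on constant hazards, 10% to 30% health-related exits by 2 years and hazard ratios of 2 to 4, none of which comes from the documents. The unclear status of 30-day deaths is a gap in the text and needs no assumption. The whole is an inexpensive improvement to a descriptive output and does not put a primary conclusion at risk.

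**What to change.** Keep time to death as planned, with four changes to the SAP.

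1. Label it as survival while in study, and show the number censored by reason: completed or administrative, versus AE, Investigator safety decision or infused prostacyclin.
2. State in Table 8-2 that deaths counted under the SAP 11.2 30-day rule are events, so that the curve and the death table agree. Let time at risk for other discontinuers run to the last date known alive within the same window, so that events and follow-up match.
3. Add one supportive Kaplan-Meier output: time to the first of death or health-related premature discontinuation, dated at exit, with other exits censored. Present it as a lower bound on survival, given that those other exits are unrelated to risk.
4. Fix the categories of health-related exit before database lock. The eCRF reason codes are not shown, and Protocol 8.1 asks only for an explanation, so free-text reasons will need a written classification rule.

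The cost is SAP wording, one derived endpoint, and one more table and figure from the recorded discontinuation date and reason. The downside is a companion curve that looks less favourable.

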9 STUDY POPULATION

9.1 SUBJECT ACCOUNTABILITY

A listing of subject disposition and inhaled treprostinil exposure will include subject number, treatment group in the parent study, first and last inhaled treprostinil dose date/time in the RIN-PH-202 study, date completed/discontinued the study, cut-off date, study drug exposure (weeks), reason for discontinuation, and any other details regarding reason for discontinuation. The summary of subject accountability will include the number (percent) of subjects by treatment group who completed the study without early termination, the number of subjects who completed inhaled treprostinil treatment by each visit achieved, the number of subjects who discontinued inhaled treprostinil treatment, and the reason for discontinuation. This summary will be provided by treatment group in the parent study and overall.

Inhaled treprostinil exposure and the total subject-years of inhaled treprostinil exposure will be summarized by treatment group in the parent study and overall.

In addition, for subjects who were in the inhaled treprostinil treatment group in the parent study (RIN-PH-201), their exposure to inhaled treprostinil in the parent study will be combined with the RIN-PH-202 study. The overall exposure to inhaled treprostinil across both the parent study and the RIN-PH-202 study will be summarized.

9.2 ELIGIBILITY CRITERIA

The listing of entry criteria for all subjects will include each subject's treatment group in the parent study, status regarding meeting all eligibility criteria (yes/no), and an explanation if not all eligibility criteria are met. The summary of entry criteria will include the number and percent of subjects who did meet and the number and percent of subjects who did not meet all eligibility criteria by treatment group in the parent study and overall.

In addition, a listing will be provided for protocol deviations. The listing will include the subject number, deviation date, deviation type, deviation severity, and deviation description by treatment group in the parent study. Deviations will be reviewed by the clinical team prior to database lock and those that might affect subject safety or efficacy outcomes will be considered "Major." All other deviations will be classified as "Minor."

9.3 OTHER DESCRIPTIONS OF STUDY POPULATION

9.3.1 *Demographics*

The listing of subject demographics will include subject number, assessment date, date of birth, subject age (years), sex, ethnicity, race, height, weight, and body mass index (BMI). Age will be calculated based on the first inhaled treprostinil dose date in the RIN-PH-202 study. The summary of demographics will include descriptive statistics for age (years) at first dose of inhaled treprostinil and categorical summaries for age (<65 years of age, 65 to <80 years of age, and ≥80 years of age), sex, ethnicity, race, height, weight, and BMI, where weight is the measure before the first dose of inhaled treprostinil for the RIN-PH-202 study and height is obtained from the parent study.

9.3.2 *Baseline Characteristics*

Baseline characteristics will include 6MWD, 6MWD category (\leq 350 m versus $>$ 350 m and \leq median Baseline 6MWD versus $>$ median Baseline 6MWD), DLCO percent predicted

(<40% versus $\geq 40\%$), NT-proBNP, and PFTs and will be summarized by treatment group in the parent study and overall. Baseline measurements are defined as the last measurement prior to the first inhaled treprostinil dose in the RIN-PH-202 study. Baseline characteristics will be included in the appropriate listings.

9.3.3 *PH-ILD History*

Information related to subjects' PH-ILD history will be listed. The listing will include the date of initial PH diagnosis, years since PH diagnosis, etiology of ILD (including idiopathic interstitial pneumonia subcategory), date of confirmatory computed tomography scan, and the date of confirmatory lung biopsy, if performed.

The current ILD diagnosis (ILD category) and time since PH diagnosis will be summarized by parent study treatment group and overall.

9.3.4 *Concomitant Medications*

All concomitant medications recorded on the eCRF will be mapped to a standard name and Anatomical Therapeutic Chemical (ATC) Levels 1 to 4 using the WHODrug Global. The ATC Levels 2 and 4 and verbatim term of all concomitant medications will be listed for all subjects. This listing will include the date started (or indication that drug was ongoing from parent study), date discontinued (or indication that drug was ongoing at end of study), and the condition(s) treated/indication(s). Summaries will be provided for medications ongoing from the parent study and for those added in the RIN-PH-202 study. Each summary will be provided by treatment group in the parent study and overall and will include the number (percent) of subjects reporting each medication by ATC Level 2 and Level 4. If ATC Level 4 is not available for a medication, ATC Level 3 will be substituted. If ATC Level 3 is not available, ATC Level 2 will be substituted. If ATC Level 2 is not available, ATC Level 1 will be substituted.

9.3.5 *Inhaled Treprostinil Dosing*

In the RIN-PH-202 study, inhaled treprostinil dosing information will be recorded whenever a change occurs in the dose. A listing and a summary will be provided for inhaled treprostinil dosing. The listing will include initial dose (number of breaths for each session and number

of breaths for the day), date of this initial dose, and dose and date of each dose change. Dosing at each analysis visit will be summarized. The summary will include both the numeric summaries and the categorical summaries for number of breaths per session as well as the number of breaths per day. If study drug is dosed differently across different sessions on the same day, the maximum number of breaths will be used for summarization. A summary of overall duration of exposure will be included, as well as the final dose (breath/session) and the maximum study drug dose (breath/session) reached for each subject (numerically and categorically).

For study treatment compliance, the number and percentage of days with dose >0 breaths will be calculated and summarized.

10 EFFICACY ANALYSES

10.1 6-MINUTE WALK TEST

The listing of the 6-Minute Walk Test (6MWT) will include subject number, analysis visit, assessment date/time (day), last inhaled treprostinil dose date/time (day), the last inhaled treprostinil dose (number of breaths), hours from last inhaled treprostinil dose to 6MWT, 6MWD results and associated changes from Baseline, use of supplemental oxygen, and any circumstances affecting the 6MWT. The summaries of 6MWD will be provided by treatment assignment in the parent study (inhaled treprostinil or placebo) and overall by visit. The summaries will include descriptive statistics for 6MWD at each analysis visit and the change from Baseline. Baseline is defined as the last 6MWD measured prior to the first dose of inhaled treprostinil in the RIN-PH-202 study. Additionally, a plot of mean change from Baseline in 6MWD at each study visit by parent study treatment group will be provided.

10.2 N-TERMINAL PRO-BRAIN NATRIURETIC PEPTIDE

NT-proBNP values and associated changes from Baseline will be listed and the listing will include subject number, analysis visit, and assessment date (day). NT-proBNP values and change from Baseline values will be summarized by parent study treatment group and overall at each analysis visit. The summary will also include the geometric mean and geometric standard deviation. Baseline is defined as the last NT-proBNP value obtained prior to the first dose of inhaled treprostinil in the RIN-PH-202 study.

10.3 ST. GEORGE'S RESPIRATORY QUESTIONNAIRE

SGRQ total and domain scores will be listed and the listing will include subject number, analysis visit, assessment date (day), and parent study treatment group. SGRQ total and domain scores and the associated changes from Baseline values will be summarized by parent study treatment group at each analysis visit. Baseline scores will be calculated from the last SGRQ administered prior to the first dose of inhaled treprostinil in the RIN-PH-202 study.

